Population: 10,449 patients aged 16-35 years in CPRD with TASD and two years follow up.

WP1: Internal and external validation of shoulder dislocation coding and treatments within a routinely collected dataset (CPRD).

WP2: Propensity score-matched cohort study using linked CPRD and HES. All events and outcomes will be collected using a pre-agreed list of READ CODES (CPRD) and OPCS 4.7 CODES (HES).

Exclusions: Surgery after more than one dislocation; instability treated with a rotator cuff repair or fracture surgery.

Intervention: Surgical repair within 6 months of first time T ASD.

Control: non-surgical intervention.

Outcomes: Rate of re-dislocation, identified by codes in CPRD for 2 years after either treatment.

Sample size: 3065 with 656 expected total number of re-dislocations (90% power, 5% significance).

Statistical analysis: Propensity scores, Cox regression modelling and Rosenbaum bounds sensitivity analysis for *Surgical versus non-surgical intervention on re-dislocation*. Multiple imputation methods, survival models and fractional polynomials for *Predictors of recurrent dislocations*.

C. Objectives, Specific Aims and Rationale

Aim 1. To study the association between surgical treatment (compared to no surgery) and recurrence rates following a first episode of traumatic anterior shoulder dislocation (T ASD) amongst young adults. **Aim 2.** To identify clinical predictors of further recurrent dislocations in young adults with traumatic anterior shoulder dislocation stratified by surgery and no surgery.

Objectives: Following the HTA commissioning brief, we plan to use routinely collected observational datasets (Clinical Practice Research Datalink (CPRD) and Hospital Episodes Statistics (HES)) to answer the research questions above. The size of routinely collected data in UK primary care (CPRD) and secondary care (HES) offers rapid observational data to uncertainties about treatments in an affordable and generalisable manner. We have planned a propensity score-matched cohort study, with the intention to minimise confounding. Propensity score matching is considered one of the best methods available to approximate to any results obtained from randomised controlled trials. To ensure further value for money and to confirm the ability of these datasets to answer this very specific commissioned question, we plan a two stage approach through Work Packages 1 and 2.

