Main study (WP2): The main study (WP2) will be a population based propensity score-matched cohort study using CPRD and HES collected datasets. The cohort of participants in this study will be young adults (aged 16–35 years) with traumatic anterior shoulder dislocation (T ASD) with at least 2 years data entry in CPRD before the their first shoulder dislocation code and at 2 years follow up from their first dislocation code entry in CPRD. All events and outcomes will be collected using a pre-agreed validated list of READ CODES (CPRD) and OPCS 4.7 CODES (HES). These codes are listed in the appendices and have already been identified. They will be further validated and informed by WP1. The first read code entry in CPRD for shoulder dislocation will be defined as the ‘first dislocation’. These codes will then be routinely linked to patients and to HES.

The ***Intervention group*** will be patients in CPRD with first time T ASD who underwent shoulder stabilisation surgery after their first dislocation (early surgical repair in this NHS context will mean ‘a decision to treat surgically after the first T ASD’ and receiving surgery within 6 months). This means linking HES data to CPRD data in such a way that a HES surgical OPCS 4.7 code is seen to occur after a single first dislocation code in CPRD (without further dislocation codes) before that surgical date. The timelines between first dislocation codes and OPCS 4.7 codes will be recorded. The ***Control group***. While the most desirable control group would be physiotherapy, it is possible that WP1 will reveal that free text notes and referral codes on physiotherapy will be lacking and not reliable. If this is the case then conservative care will be defined as ‘non surgical intervention’ with no linked OPCS 4.7 surgical shoulder codes producing a control cohort of patients whose first time shoulder dislocation has been treated non-operatively. If however free text entries and referral codes for physiotherapy are reliably present in CPRD then conservative care will be physiotherapy identified by physiotherapy referral codes after a first time T ASD code. Any subsequent dislocation codes or OPCS 4.7 surgery code will be recorded.

This project was funded by the National Institute for Health Research Health Technology Assessment (project number 14/160/01).

The views and opinions expressed therein are those of the authors and do not necessarily reflect those of the HTA, NIHR, NHS or the Department of Health.

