This commissioned call is directed at 'younger adults'. From age 40 years onwards instability and dislocation is associated with rotator cuff tears and the pathology and outcomes are different. Rotator cuff tears are highly rare below age 35 years and so our young target population will be patients aged 16-35 years in CPRD with a first time T ASD who underwent stabilisation surgery within 6 months of their first dislocation. We require a total sample size of 3065 with 656 expected total of re-dislocations. There are 26,534 patients in CPRD with recurrent anterior shoulder dislocations, and at least 10,449 of these patients will be aged 16-35 years with T ASD [7].

Inclusion criteria: Patients aged 16-35 years of age with a first time traumatic anterior dislocation (T ASD); patients that can be linked by CPRD and HES; minimum two year follow up period in CPRD.

Exclusion criteria: Surgery after more than one dislocation; instability treated with a rotator cuff repair or fracture surgery. We will also exclude:

- Patients aged 16-35 years with first time T ASD who cannot be linked by CPRD-HES
- Patients with less than two year follow up in CPRD
- Surgery after more than one T ASD
- Instability treated with rotator cuff repair surgery or fracture surgery.

J. Selection of comparison group(s) or controls

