The ***Intervention group*** will be patients in CPRD with first time T ASD who underwent shoulder stabilisation surgery after their first dislocation (early surgical repair in this NHS context will mean 'a decision to treat surgically after the first T ASD' and receiving surgery within 6 months). This means linking HES data to CPRD data in such a way that a HES surgical OPCS 4.7 code is seen to occur after a single first dislocation code in CPRD (without further dislocation codes) before that surgical date. The timelines between first dislocation codes and OPCS 4.7 codes will be recorded. The ***Control group***. While the most desirable control group would be physiotherapy, it is possible that WP1 will reveal that free text notes and referral codes on physiotherapy will be lacking and not reliable. If this is the case then conservative care will be defined as 'non surgical intervention' with no linked OPCS 4.7 surgical shoulder codes producing a control cohort of patients whose first time shoulder dislocation has been treated non-operatively. If however free text entries and referral codes for physiotherapy are reliably present in CPRD then conservative care will be physiotherapy identified by physiotherapy referral codes after a first time T ASD code. Any subsequent dislocation codes or OPCS 4.7 surgery code will be recorded.

K. Exposures, Outcomes and Covariates

As part of this application, we have performed a consensus survey of specialist shoulder surgeons and shoulder physiotherapists who are all members of the British Elbow and Shoulder Society. Saturation point and a list of predictors was reached rapidly and this list is tabulated in Appendix E and highlights the risk factors (and covariates) deemed most important. It is unlikely that all of these will be available from routinely collected national datasets but our study design will allow us to confirm through WP1 those factors that are reliably collected and that can be used for full analysis in WP2.

L. Data/ Statistical analysis

The association of surgical versus non-surgical intervention on subsequent re-dislocation within 2-years. The primary outcome of interest is the time from a first time traumatic anterior dislocation to subsequent re-dislocation within 2-years. The exposure of interest is whether or not a patient received shoulder surgery. In randomized controlled trials each person has

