This project was funded by the National Institute for Health Research Health Technology Assessment (project number 14/160/01).

The views and opinions expressed therein are those of the authors and do not necessarily reflect those of the HTA, NIHR, NHS or the Department of Health.

an equal probability of being in a treatment or control group. Observational study designs are limited by an inherent imbalance of both known and unknown confounders making some patients more likely to receive surgery than others. As the type of surgery received is not randomly allocated in our study, confounding by indication will be accounted for by using propensity score matching methods. Use of these methods for the assessment of causality in epidemiological studies has been previously described[1]. The propensity score represents the probability that a patient received the intervention (surgery). A logistic equation is fitted where the outcome is surgical intervention versus non-surgical; and any covariates are introduced as potential confounders of subsequent dislocation. We have already identified an expert consensus list of all potential confounders of interest (Appendix E)

Propensity scores are used to match each patient receiving surgery to comparable non-surgical controls using a caliper width of 0.2 standard deviations of the logit of the propensity score[2]. This is a standard method for minimizing confounding by indication, which not only balances observed baseline characteristics in both surgical and non-surgical groups, but also eliminates surgical patients with no comparable controls[3].

Immortal time bias is a common issue in epidemiological studies, where the event of interest cannot occur for a certain time span. In the case of this proposed study immortal time bias would occur due to the definition of exposure, where in the time from first dislocation till receipt of surgery those in the 'surgical arm' cannot have the outcome by design otherwise they would have been classified as non-surgical. To avoid the problem of immortal time bias, we will use time varying exposures, where in a survival analysis the time period previous to the index date of surgery is reclassified as non-surgical for those in the surgical intervention group.

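### The fallback control group is selected on later surgery: patients stabilised after 6 months fit neither group, operated re-dislocators are also removed, and the net bias in the hazard ratio has unknown sign

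*Protocol*

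**What the plan says.** **Intervention.** Section B gives "Intervention: Surgical repair within 6 months of first time T ASD". Sections F and J add that the "HES surgical OPCS 4.7 code is seen to occur after a single first dislocation code in CPRD (without further dislocation codes) before that surgical date".

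**Control.** Sections F and J give two definitions and leave the choice to the validation stage (WP1). The preferred one applies if physiotherapy coding is reliable: "then conservative care will be physiotherapy identified by physiotherapy referral codes after a first time T ASD code". It states no surgery-free condition. The fallback takes patients "with no linked OPCS 4.7 surgical shoulder codes producing a control cohort of patients whose first time shoulder dislocation has been treated non-operatively", with no time limit on the surgical code. Both sections add that later dislocation or surgery codes will be recorded, but not what follows from them.

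**Exclusions.** Section I lists "Surgery after more than one T ASD", rotator cuff or fracture surgery, failed linkage and less than two years of follow-up.

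**Analysis.** Section L says "The exposure of interest is whether or not a patient received shoulder surgery". Its immortal-time remedy is that "the time period previous to the index date of surgery is reclassified as non-surgical for those in the surgical intervention group". The primary outcome is time from first dislocation to re-dislocation within 2 years.

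**The concern.** Follow one patient through the document: one dislocation, no recurrence, stabilisation at month 9.

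- Intervention group: no, because the operation falls outside 6 months.
- Fallback control: no, because a surgical code is linked.
- Exclusion list: not covered, because surgery followed a single dislocation.
- Physiotherapy control: yes if referred, with post-operative time apparently counted as non-surgical.
- Section L exposure: surgical, if the sentence on exposure is read literally.

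Under the fallback definition, nine event-free months of non-surgical care disappear because of something that happened later. A second set is lost in the same way: controls who re-dislocated and were then operated on. They have a linked code, and section I excludes them as well. Every one of them is a control event.

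Both losses fall on the non-surgical side and both depend on the future. Propensity matching on baseline covariates cannot repair selection on a post-baseline event. The section L sensitivity analysis concerns early re-dislocation after surgery and does not address it. What is at stake is the primary hazard ratio.

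**Working it through.** **Inputs from section G.** Two-year re-dislocation risk of 25% without surgery and 20% with surgery; hazard ratio 0.78.

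**Assumptions, not in the documents.**
- q: share of never-re-dislocated controls stabilised late.
- s1: the same group as a share of all controls, so s1 = 0.75q.
- s2: share of control re-dislocators later operated on and so removed.

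**Plan's own figure.** Under proportional hazards, HR = ln(1 − p_surg)/ln(1 − p_control). Then ln(0.80)/ln(0.75) = 0.7757, which matches the stated 0.78.

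**Step 1: loss of event-free late-surgery patients only (s2 = 0).** Apparent control risk = 0.25/(1 − 0.75q).
- q = 10%: 0.25/0.925 = 27.0%. A true null appears as ln(0.75)/ln(0.730) = 0.91, and the planned 0.78 as 0.71.
- q = 20%: 0.25/0.85 = 29.4%. A true null appears as 0.83, and the planned 0.78 as 0.64.

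These are ceilings, because the formula treats every removed patient as someone who would have stayed event-free to 24 months. A simulation of 2 million patients with exponential times, and late surgery between 6 and 24 months unrelated to risk, lets some of them be future re-dislocators. With 8.4% of patients removed it gives 26.3%, against 0.25/(1 − 0.084) = 27.3% by formula. With 16.8% removed it gives 27.9%, against 0.25/(1 − 0.168) = 30.0%.

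**Step 2: add the loss of operated re-dislocators.** Apparent control risk = 0.25(1 − s2)/(1 − s1 − 0.25·s2). The bracketed figure is the hazard ratio that would appear if the surgical risk is 20% (true value 0.78).

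| | s2 = 0 | s2 = 10% | s2 = 20% | s2 = 30% |
|---|---|---|---|---|
| s1 = 5% | 26.3% (0.73) | 24.3% (0.80) | 22.2% (0.89) | 20.0% (1.00) |
| s1 = 10% | 27.8% (0.69) | 25.7% (0.75) | 23.5% (0.83) | 21.2% (0.94) |

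**Step 3: break-even.** Let a share r of controls be removed, of whom a fraction f had re-dislocated first. The apparent risk is (0.25 − r·f)/(1 − r), which exceeds 0.25 only if f < 0.25. So the control rate is inflated when fewer than a quarter of the removed patients had re-dislocated, and deflated when more had.

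**Step 4: how wide this could be.** Section G cites 17/61 = 27.9% subsequent surgery in non-surgical trial arms, without saying how many had re-dislocated first. Using r = 0.279 purely as an illustration:
- f = 0: 0.25/0.721 = 34.7%
- f = 0.25: 25.0%
- f = 0.5: (0.25 − 0.1395)/0.721 = 15.3%

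**Step 5: repairing one side only.** With s2 = 20%, restoring the event-free late-surgery patients while keeping the exclusion of operated re-dislocators gives 0.20/0.95 = 21.1%. Before that repair the figure was 23.5% (s1 = 10%) or 22.2% (s1 = 5%). In both cases the half-repair moves further from 25%.

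**Step 6: repairing both sides.** In the simulation, keeping everyone, counting every re-dislocation before surgery and censoring at late surgery returns 25.0%, provided late surgery is unrelated to risk.

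All of this is crude cohort arithmetic. It does not reproduce the matched-set stratification or the frailty term.

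**The case against.** A reader might infer from Step 1 alone that the control rate is inflated and that early surgery will look protective even if it is not. The documents do not support that. The rule that drops the event-free month-9 patient also drops the operated re-dislocator, and the exclusion in section I reinforces the second loss. The protocol gives no split between the two. Section G moves between subsequent surgery and re-dislocation at the same 25% and 20%, which if anything suggests that its writers expect later surgery to follow recurrence.

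Three further points can fairly be made.

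- **Section L is ambiguous.** If its exposure sentence makes the late-surgery patient surgical, the time-varying rule would return the pre-operative months. If that rule applies only to the intervention group as defined in F and J, it would not. This stands: the text does not settle it, so the loss of person-time is likely under the fallback definition but not certain.
- **The mechanism is conditional.** Physiotherapy is the preferred comparator, and no removal for later surgery is stated there. This also stands. The defect there is different: post-operative time with no rule to take it out of the non-surgical state.
- **Censoring rules commonly sit in a statistical analysis plan, and section F promises an updated analysis plan before WP2.** This carries less weight. The protocol itself states twice who is a control, and a later censoring rule cannot restore patients whom that definition has already left out.

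**Conclusion.** The gap is real. Under the fallback definition, control membership is decided by a future event, patients stabilised after 6 months following one dislocation belong nowhere, and controls operated on after re-dislocation are removed with their events.

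The two losses pull in opposite directions. The first alone lifts a 25% control risk to at most 27.0% or 29.4% for q of 10% or 20%. Adding the second can bring it below 25%: with s1 = 5% and s2 = 30% the planned effect disappears (apparent hazard ratio 1.00). The sign turns on whether more or fewer than 25% of the removed patients had re-dislocated first, and the documents do not say. Offsetting biases of unknown size give no assurance that they cancel.

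The shares q, s1 and s2 are assumed throughout. The conclusion that the sign is undetermined does not depend on any particular value of them.

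**What to change.** The two parts below must be made together, because Step 5 shows that the first half alone can worsen the bias.

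1. **Sections F, I and J.** Stop using later surgery to decide control membership. Drop the open-ended condition of no linked surgical code, and do not apply the exclusion for surgery after more than one dislocation to the non-surgical comparison. It can still help to define who counts as having had the intervention.
2. **Section L.** Let every eligible patient contribute non-surgical time from the first dislocation. Count a re-dislocation before any surgery as a non-surgical event. Censor event-free patients at a first stabilisation after 6 months. As a sensitivity analysis, move their later time to the surgical state instead. State that these rules hold under either control definition, so that post-operative time of physiotherapy controls is also covered.

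Sections B, F, I, J and L then need to be reconciled so that group, exclusion and exposure use the same rule.

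**Cost.** Protocol wording and one rule in building the survival data set. The pause between WP1 and WP2, when an updated analysis plan is due, is a natural time. **Downside.** Censoring at late surgery may be informative if those operated on late differ in risk; the sensitivity analysis examines this but does not remove it.

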Work Package 1: Data Validation of shoulder dislocation coding and treatments within a routinely collected dataset (CPRD). **Work Package 2:** Population based cohort study using routinely collected datasets (CPRD and HES).

Having run feasibility counts in CPRD and there are 26,534 patients with shoulder dislocations in the database. We expect at least 10,449 to be T ASD in 'young' patients aged 16-35 years of age [7] indicating a very substantial dataset to answer this commissioned call.

D. Background

This project and study has been commissioned by the HTA and as such has already been deemed necessary. We can confirm that since the commissioned call there have been no published systematic reviews, or RCTs that answer the commissioning brief.

Shoulder joint dislocations are the most common joint dislocations seen in hospital A+E departments (8.2-17 cases per 100,000 population/year) with 95% of traumatic glenohumeral dislocations being anterior [15]. Traumatic anterior shoulder instability can carry significant morbidity. Some in the clinical community still quote high re-dislocation rates of 85% [16] and 92% [17] despite more recent larger population studies. A small but highly cited Swedish population study was conducted by Hovelius [18]. This prevalence study was in a random sample of 2092 people aged 18 to 70 years. 1.7% of patients reported a history of dislocation. There was a male to female ratio of 3:1 overall but this ratio varied with age being 9:1 in the 21 to 30 years age group. Hovelius also looked at recurrent dislocation trends

This project was funded by the National Institute for Health Research Health Technology Assessment (project number 14/160/01).

The views and opinions expressed therein are those of the authors and do not necessarily reflect those of the HTA, NIHR, NHS or the Department of Health.

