Using data from a Cochrane systematic review comparing surgical to non-surgical treatment for acute T ASD [6]; from the pooled results 3/58 patients in the surgical arm had subsequent further surgery (5.17%) compared to 17/61 in the non-surgical arm (27.9%) at a minimum follow up of 2-years (Risk Ratio 0.22, 95% CI 0.08 to 0.64). The large effect size is set in the context of the pooled results of 3 RCTs with uncertainty around the true size of the effect outside of a clinical trial setting in routine general practice. Conservatively, we would look to detect a smaller difference in subsequent surgery within 2-years of 25% in the non-surgical group, compared to 20% in the surgical group (an absolute difference of 5%). A 2-sided log rank test for equality of survival curves, with 90% power at 5% significance level (alpha), where outcome is time to re-dislocation, with an anticipated 25% re-dislocation rate in the non-surgical control group compared to a 20% in the surgical group (equivalent to a hazard ratio of 0.78), allowing for 10% loss to follow up and assuming equal group sizes, we require a total sample size of 3065 with 656 expected total of re-dislocations. There are 26,534 patients in CPRD with recurrent anterior shoulder dislocations, and at least 10,449 of these patients will be aged 16-35 years with T ASD [7]. The study will therefore be adequately powered. ***See flow diagram in appendix for estimation of numbers.***

H. Data Linkage Required (if applicable)

Data linkage and data management for our proposed study involves 2 different data sources (CPRD and HES). They need to be linked to answer the aims of WP2 as stated above. We have therefore included co-applicants with extensive experience in the use of linked datasets. The data management needed to produce a final working dataset will be carried out by a senior data manager at Oxford with expertise in such procedures. Under supervision from the application team, the data manager will develop ad-hoc code in Python and SQL to produce a dataset that can be analysed using standard statistical packages such as Stata.

I. Study Population

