Matched surgical patients and their non-surgical controls will then be included in a Cox regression survival model to describe the association between receipt of surgery and time to subsequent dislocation within 2-years. The model is stratified on matched sets, to allow for the correlation between matched pairs of surgical patients and controls. As clustering exists within the data (patients nested within GP practices), a multilevel survival model will be fitted by extending the Cox regression model to include a frailty term with a Gaussian distribution[8]. This will allow adjustment for evidence of unexplained variation across GP practices. To assess the potential effect of unmeasured confounders we will conduct a Rosenbaum bounds sensitivity analysis[9]. This provides an estimate of the magnitude of hidden bias that would have to be present to explain the associations actually observed. The proportional hazards assumption will be assessed using Schoenfeld's residuals. Kaplan-Meier plots will be used to estimate the probability of survival up to 2-years in surgical and non-surgical groups.

Identifying predictors of recurrent dislocations

Using the CPRD-HES linked dataset we will develop a prediction model to identify patients at increased risk of subsequent re-dislocation. Potential risk factors will include all those described above. The cumulative effect of missing data in several variables often leads to exclusion of a substantial proportion of the original sample, causing a loss of precision and power. To overcome this bias we will use multiple imputation methods, which allows for the uncertainty about missing data by creating several plausible imputed datasets and appropriately combining their results [10, 11].

Survival models (Cox regression) will be used to identify risk factors associated with time to re-dislocation. Backward selection methods will be used to identify risk factors and shrinkage methods applied to adjust for over fitting. Continuous predictors will be examined using fractional polynomials and clinically plausible interaction terms will be tested for inclusion (specifically whether the predictors differ in the surgical and non-surgical intervention groups). For internal validation of the model we will use a combination of multiple imputation and bootstrapping[12-14].

Performance of the model will be assessed in terms of calibration and discrimination[11, 23]

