APPENDIX F

METHOD FOR LINKAGE OF CPRD AND HES DATASETS

CPRD data is linked to HES using the HESID identifier. Over 60% of the CPRD population is currently linked to HES. The linkage of CPRD to HES data is a 2-step process: (1) The creation of a unique and anonymous ID in HES for each patient (HESID), and (2) Linkage of CPRD to HES using the HESID index. The detailed protocol on creating a HESID is publicly available online (http://www.hscic.gov.uk/media/1370/HES-Hospital-Episode-Statistics-Replacement-of-the-HES-patient-ID/pdf/HESID_Methodology.pdf).

In summary the majority of hospital admission episodes are linked using a combination of sex + date of birth (dob) + NHS number (step 1) OR sex + dob + [postcode + local hospital generated patient identifier] (step 2). Since 2009 a third step was added to try and increase the linkage in early years where NHS number was less completely recorded. This allows for a match on sex + dob + postcode, but only where this does not lead to a HESID being associated with 2 different NHS numbers, and only where the postcode is not on the list of known communal establishments (nursing homes, army barracks, prisons). In the past 10 years, NHS number has been complete for >95% of all records so the HESID should be particularly reliable during this period. Efficiency of the HESID algorithm may have been lower in earlier years when the completeness of recording of NHS number was lower.

Linkage CPRD-HES using the HESID: HES use a standard 8 pass algorithm to link HES to CPRD data via the HESID index (Detailed information is available online at http://www.hscic.gov.uk/media/11668/HES-ONS-Mortality-Data-Guide/pdf/guide_to_linked_ONS_HES_mortality_data_V4_040613.pdf).

The 8 passes involved are:

Pass 1 - Exact NHS, sex, DoB, Postcode

Pass 2 - Exact NHS, sex, DoB,

Pass 3 - Exact NHS, SEX, postcode, partial DOB

Pass 4 - Exact NHS, SEX, partial DOB

Pass 5 - Exact NHS, postcode

Pass 6 - Exact sex, dob and postcode (where NHS doesn't contradict the match, DOB not 1st of January & postcode not on the ignore list)

Pass 7 - Exact sex, DOB and postcode (where NHS doesn't contradict the match and dob is not 1st of January)

Pass 8 - Exact NHS

After this whole process, CPRD only keeps matches that are identified in passes 1 through 5. This means that the match must be on NHS number plus at least one other piece of information (and in most cases 2 other pieces).

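### The 90% power at 3,065 patients and 656 re-dislocations belongs to an unpaired log-rank test; the matched-set, time-varying Cox model in Section L has less at that size, and some Section G inputs conflict with other sections

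*Protocol*

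**What the plan says.** Section G assumes two-year re-dislocation risks of 25% without surgery and 20% with surgery (hazard ratio 0.78), equal groups, 10% loss to follow-up, 90% power and two-sided 5% significance in a log-rank test. It states that "we require a total sample size of 3065 with 656 expected total of re-dislocations", sets this beside 10,449 eligible patients and concludes that power is adequate, referring to the Appendix B flow diagram for the numbers.

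The analysis in Section L is different. Surgery is a time-varying exposure, with the period before surgery reclassified as non-surgical, and the Cox model is fitted to matched patients: "The model is stratified on matched sets, to allow for the correlation between matched pairs". The outcome in Section L runs from first dislocation; the Technical Summary counts two years after either treatment.

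Three inputs bear on the same calculation:

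- Section G introduces the target as a "smaller difference in subsequent surgery within 2-years of 25% in the non-surgical group", then uses the same percentages as re-dislocation rates.
- Section I excludes "Patients with less than two year follow up in CPRD".
- Section G says "There are 26,534 patients in CPRD with recurrent anterior shoulder dislocations", and Section I repeats it. Section C says "there are 26,534 patients with shoulder dislocations in the database".

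**The concern.** A power figure is useful only if it describes the analysis that will be run. In a Cox model stratified on pairs, an event contributes only when both members are still at risk and their exposure differs. If the control re-dislocates before the partner's surgery date, both members are unexposed and the pair says nothing about surgery. After the first event in a pair, the survivor has no comparator. Section G counts all such events at full value.

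At stake is how 3,065 is read. It appears in the Technical Summary and in Sections G and I as the size that secures 90% power. Comparing it with 10,449 does not test feasibility, because with equal groups the limiting number is surgical patients who are linked to HES and can be matched.

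The input conflicts matter in their own right. Excluding patients with under two years of follow-up makes loss within two years of first dislocation impossible, so a 10% allowance for it is incoherent. The same rule discards observed events, for example a patient who re-dislocates at 3 months and leaves the practice at 18 months.

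**Working it through.** **Inputs from the protocol.** Risks 25% and 20%, 10% loss, equal groups, 90% power, two-sided 5% (Section G); surgery within 6 months (Sections F and J); 35% receiving surgery and 20% lost in matching (Appendix B notes); "Over 60% of the CPRD population is currently linked to HES" (Appendix F).

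**Assumptions not in the protocol.** Constant hazards, 1:1 matching, independent outcomes within pairs, and a distribution of surgery times, shown as a range. The practice frailty term is left out.

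**Reproducing Section G** (time unit: two years)

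- Hazards: λ0 = −ln 0.75 = 0.2877; λ1 = −ln 0.80 = 0.2231; loss c = −ln 0.90 = 0.1054.
- HR = 0.2231/0.2877 = 0.7757; ln HR = −0.2540.
- Events: Schoenfeld 4(1.960 + 1.282)²/0.2540² ≈ 651; Freedman ≈ 658. The stated 656 lies between them.
- Event probability with exponential loss, λ/(λ + c) × [1 − exp(−(λ + c))]: 0.2379 and 0.1902, mean 0.2140.
- 656/0.2140 = 3,065.

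The stated figures are right for an unpaired log-rank test.

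**The stated model at 1,532 pairs.** For surgery at time s and end of follow-up T, the chance that a pair is informative is

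exp(−(λ0 + c)s) × (λ0 + λ1)/(λ0 + λ1 + 2c) × [1 − exp(−(λ0 + λ1 + 2c)(T − s))].

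T = 1 if the clock starts at dislocation and 1 + s if it starts at surgery. Power is Φ(0.2540 × √d/2 − 1.960), where d is the number of informative pairs.

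Example: all surgery at 6 months (s = 0.25), no loss, clock from dislocation. The chance is 0.9306 × 0.3183 = 0.2962, so d = 1,532 × 0.2962 = 454 and power = Φ(2.706 − 1.960) = 77%.

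| Clock | Surgery timing | 10% loss: pairs, power | No loss: pairs, power |
|---|---|---|---|
| Either | At time zero (stratification alone) | 558, 85% | 613, 88% |
| From dislocation | Uniform 0–6 months | 484, 80% | 533, 83% |
| From dislocation | Uniform 3–6 months | 447, 77% | 493, 81% |
| From dislocation | All at 6 months | 411, 73% | 454, 77% |
| From surgery | Uniform 0–6 months | 531, 83% | 591, 87% |
| From surgery | All at 6 months | 505, 81% | 570, 86% |

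An 8,000-replicate simulation of the dislocation-clock rows agreed to within about one percentage point.

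**Pairs needed for 90%** (651 divided by the informative fraction): about 1,870 to 2,430 from dislocation and 1,690 to 1,970 from surgery, over uniform 0–6 months to all at 6 months, with and without loss.

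**Supply on the plan's own shares**

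- 10,449 × 0.35 × 0.80 = 2,926 pairs, about 5,850 patients.
- With 60% linkage still to apply: 2,926 × 0.60 = 1,755 pairs, about 3,510 patients.

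At 1,755 pairs, over the same two timings, power is about 79 to 88% from dislocation and 86 to 91% from surgery. At 2,926 pairs it is about 94% or more throughout.

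**The case against.** Sizing a study with a simpler test than the final model is common, and 3,065 is a minimum for a retrospective database rather than a recruitment cap. That stands. A reader might infer an arithmetic slip from the mismatch, but there is none: 3,065, 656 and the hazard ratio all reproduce.

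A reader might also infer that the study is underpowered. The documents do not support that. The plan's own shares give more matched patients than 3,065 even after a 60% linkage factor, and that factor is a floor. Section G relies on a flow diagram that is not visible here; its notes already apply the surgery share and the matching loss, so whether linkage was also applied cannot be checked.

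Nor can one power figure be attached to the stated model. The protocol gives no surgery-time distribution, refers to both a single control and plural controls per surgical patient, and uses two time origins. If the follow-up exclusion stays, only the no-loss column applies on the dislocation clock, which is the more favourable one. As regards power, the 10% allowance is therefore conservative.

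Two further inferences should be resisted. Appendix D's counts of recurrent codes do not settle what 26,534 means, because they count clinical events, not patients; the clash between Section C and Sections G and I is enough. And lower power does not by itself make pair stratification the wrong model; changing it would be a trade-off.

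What remains is that no scenario tried reaches 90% at 1,532 pairs, and that the input conflicts are visible on the page.

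**Conclusion.** The point holds in a limited form. The 90% claim at 3,065 patients is correct for the log-rank test in Section G and unsupported for the analysis in Section L. At that size the stated model has roughly 73 to 83% power counting from first dislocation and 81 to 87% counting from treatment. These ranges assume 1:1 matching, independent outcomes within pairs, constant hazards, hazard ratio 0.776 and surgery spread between the two timings shown.

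A study-level shortfall is not shown. Whether 90% is reached depends mainly on whether HES linkage still has to be taken off the 10,449, and on the time origin: 1,755 pairs straddle the target, while 2,926 pairs exceed it.

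The three inconsistencies hold without modelling: 10% loss against the two-year follow-up exclusion, subsequent surgery against re-dislocation as the basis of the 25% and 20%, and two descriptions of the same 26,534 patients.

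**What to change.** 1. Restate the power at 3,065, or the number of matched pairs needed for 90%, for the matched-set, time-varying Cox model. State the matching ratio, the surgery-timing assumption and one time origin, and give the result as a range. Compare it with the expected number of linked, matched surgical patients, not with 10,449.
2. Replace the exclusion of patients with under two years of follow-up by censoring at transfer out, death or last data collection. This keeps observed early re-dislocations and makes the 10% loss allowance coherent. If the exclusion is kept, drop the allowance.
3. Present 25% and 20% as assumed re-dislocation risks, and say that the pooled trial figures quoted before them concern subsequent surgery.
4. Correct the description of the 26,534 patients in Sections G and I to agree with Section C.

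The cost is protocol wording, a rerun sample-size calculation and a changed cohort-extraction rule; no new data source is needed. The quoted power at 3,065 becomes less favourable. Section F already schedules an updated analysis plan before Work Package 2, which is a natural place for these changes.
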